- Up to 117 weeks.
- 65 weeks for participants who are or have been diagnosed with TB treatment failure or recurrence and are or have been referred to six months of local SOC treatment by the national/local TB program.

Arm 2: 65 weeks

Arm C: 65 weeks

3. Section SCHEMA, REGIMEN

The following paragraph has been included to add three months of rifampicin/isoniazid for Arm 1 participants who are currently receiving the experimental 3-month treatment regimen as of 16Jun2023. The treatment regimen for all other participants will remain the same.

Arm 1 participants receiving the experimental 3-month treatment regimen as of 16Jun2023:
rifapentine/isoniazid/pyrazinamide/ethambutol (PHZE) + clofazimine (CFZ) 300 mg once daily for 2 weeks; then PHZE + CFZ 100 mg once daily for 6 weeks; then rifapentine/isoniazid/pyrazinamide (PHZ) + CFZ 100 mg once daily for 5 weeks; then rifampicin/isoniazid (RH) for 13 weeks for a total of 26 weeks of study treatment.

4. Section 1.4, Exploratory Objectives

The following objective has been added to align with the addition of Drug-Susceptibility Testing and Sputum AFB Smear and Culture at weeks 91 and 117:

1.4.8 To explore long term outcomes in Arm 1 participants through 117 weeks after randomization.

5. Section 3.0, STUDY DESIGN

The following update to the Arm 1 regimen and follow-up has been added to the end of the section:

Updates following the DSMB reviews in April and June 2023

Following the DSMB reviews in April and June 2023, and the premature closure to accrual of the study, Arm 1 treatment duration and follow-up was revised for participants who are currently on or have completed Arm 1 study treatment without experiencing treatment failure or TB recurrence, and have not already been referred to six months local SOC treatment. Participants in Arm 1 who have not already been referred to six months local SOC treatment will have follow-up extended through week 117.

6. Section 6.1, Schedule of Evaluations

A new Table 6.1-2 has been inserted for the additional visits and assessments for Arm 1 after week 26. The SOE table for Arm C has been renumbered to Table 6.1-3.

Table 6.1-2: Schedule of Evaluations for Arm 1 Who Have Not Been Referred to Local SOC, Additional Visits and Assessments After Week 26

| Evaluation | Follow-up | | | | | | | | | After Week 65 | |

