## 2 Study Overview

### 2.1 Overview of Study Design

A5362 is an open-label, randomized phase IIc study to evaluate whether a 3-month regimen of rifapentine/isoniazid/pyrazinamide/ethambutol (PHZE) with clofazimine (CFZ) dosed as 100 mg daily with a 2-week 300 mg daily loading dose is superior to the standard of care (SOC) 6-month regimen of rifampin/isoniazid/pyrazinamide/ethambutol (RHZE) for DS-TB with respect to (1) early bacteriologic efficacy defined as time to culture conversion by 12 weeks post-randomization and (2) safety over 65 weeks.

Participants will be randomized to one of three treatment arms; Arm 1 with treatment for 13 weeks (including a 2-week CFZ loading dose of 300 mg daily; Arm 2 with treatment for 26 weeks; or Arm C with treatment for 4 weeks with an experimental regimen and the remaining 22 weeks with SOC (PK subgroup)).

- Arm 1 (Experimental): PHZE + CFZ 300 mg once daily for 2 weeks, PHZE + CFZ 100 mg once daily for 6 weeks; then PHZ + CFZ 100 mg once daily for 5 weeks
- Arm 2 (SOC): RHZE for 8 weeks; then RH for 18 weeks
- Arm C (PK subgroup): PHZE + CFZ 100 mg once daily for 4 weeks; then on study, off study medications and treated according to SOC (RHZE for 4 weeks; RH for 18 weeks)

We will follow all participants in Arms 1, 2, and C from randomization to week 65 for the primary and secondary objectives. Protocol v2.0 LOA #1 also includes extended follow-up for some participants corresponding to new exploratory objectives which will be detailed in a separate SAP.

Participants who consent to intensive PK sampling visits will be randomized to Arms 1, 2, or C in a 2:1:1 ratio, respectively, while participants who do not consent to intensive PK sampling will be

randomized only to Arms 1 or 2 in a 2:1 ratio, respectively. We will stratify randomization based on HIV status and the presence of advanced disease as determined by chest X-ray. We will balance randomization by institution.

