##### Unfavorable Outcome

- Absence of cure. A participant will be considered to have absence of bacteriological cure if a sputum sample obtained at or after end of treatment for Arm 1 (week 13), or at or after week 17 for Arm 2 is culture-positive in liquid or solid media for an *Mtb* strain genotypically matched with the initial isolate. A second sputum sample, obtained at least four hours following the first sputum collection (see section 6.2.3 of protocol), is required to confirm absence of bacteriological cure.
- Participants who die from any cause during study treatment or follow-up except from violent or accidental cause (e.g., road traffic accident).

- Participants who had a positive culture for *Mtb* when last seen, whether confirmed by a second sample or not, unless determined to have been re-infected.
- Participants experiencing extension of treatment beyond the nominal level (week 13 for Arm 1 and week 26 for Arm 2) due to clinically inadequate response. These cases should be managed individually in conjunction with and after having notified the A5362 Clinical Management Committee (CMC). Extension of treatment to make up missed doses will not count as unfavorable.

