#### Unfavorable Outcome

Same as in outcome measure 3.2.1 A, and:

- Participants lost to follow-up during treatment phase of each Arm (i.e., 13 weeks and 26 weeks for Arms 1 and 2, respectively).
- Participants failing to complete treatment (see below for Definitions of Adequate Treatment) and not assessable at the end of the follow-up period.
- Participants receiving any one or more of the following:
  - extension of treatment beyond the nominal level, except to make up missed doses
  - a re-start of treatment following  $\geq 30$  consecutive days lost to follow-up
  - a change in at least one drug in treatment regimen for any reason except re-infection, pregnancy, or temporary drug challenge.

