3.2.3 QT interval

We derive the outcome measures defined below from ECG readings, which the site conducts in triplicate (three ECGs 5-10 minutes apart). We will use the mean of all measurements (up to 3) that are readable and available.

3.2.3.1 Mean baseline QTcF and change from baseline in mean QTcF at weeks 2, 8, and end of treatment (EOT) (Arm 1, week 13; Arm 2, week 26)

3.2.3.2 Occurrence of absolute QTcF  $\geq 480$  ms and  $< 500$  ms, and  $\geq 500$  ms, at any time during study treatment

3.2.3.3 Occurrence of QTcF change from baseline of  $\geq 30$  ms and  $< 60$  ms, and  $\geq 60$  ms, at any time during study treatment

3.2.4 Time to stable culture conversion in liquid and solid media through week 65

Defined as the first of two (consecutive or non-consecutive) negative sputum cultures without an intervening positive culture, and/or visits wherein the participant is unable to produce sputum and has no signs of active TB. Conducted separately for liquid and solid media.

3.2.5 Proportion of participants with culture conversion at weeks 8 and 12 across all study arms.

Liquid (MGIT) and solid media analyzed separately.

3.2.6 Time (days) to positivity in liquid culture (MGIT) after start of treatment through week 65

We will report the median (Q1, Q3) times to positivity in liquid culture at each time point (weeks 1, 2, 3, 4, 6, 8, 10, and 12) in Arm 1 and Arm 2.

3.2.7 Change in chest X-ray (CXR) score from baseline to end of treatment (EOT).

Sites conduct the baseline chest X-ray during screening. We will compute the chest X-ray score with the following validated formula (Ralph et al. Thorax 2010):

CXR Score = percent of total lung affected by any pathology + 40 (if cavitation is present).

We will compute the CXR scores based on both site assessment of the chest X-ray and an assessment by independent central reviewers blinded to study treatment.

- 3.2.8 Proportion of participants with one or more serious adverse events (SAEs) through week 65
- 3.2.9 Proportion of participants who have a TB relapse from EOT until week 65  
For participants who had successful culture conversion through the end of study treatment, TB relapse is defined as a recurrence of TB emanating from the same strain as the participant's originally diagnosed TB, which will be determined through molecular genotyping.

- 3.2.10 Proportion of participants who have a TB recurrence from EOT until week 65
- 3.2.11 Plasma pharmacokinetic parameters for CFZ

Arm 1

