The following intercurrent events are relevant to the estimand:  Intercurrent events that occur during therapy: 
 
1. Death except from violent or accidental cause (e.g., road traffic accident) Unfavorable outcome* (Composite strategy)
 
2. Violent or accidental death Unevaluable outcome* (Composite strategy)
 
3. A re-start of therapy following <math>\geq 30</math> consecutive days without therapy Unfavorable outcome (Composite strategy)
 
4. A change in at least one drug in treatment regimen for any reason except re-infection, pregnancy, or temporary drug challenge. Unfavorable outcome (Composite strategy)
 
	Participants lost to follow-up during the treatment phase are considered to have an unfavorable outcome (regardless of TB culture result at the last available visit) and the event time is the time of the last visit.  Participants failing to complete treatment and not assessable at the end of the follow-up period are considered to have an unfavorable outcome and the event time is the time of the last treatment dose received.  Participants receiving an extension of treatment, re-start of treatment, or change in treatment (see full definition B of unfavorable outcome) are considered to have an unfavorable outcome and the event time is the time of the treatment modification.

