
5. Pregnancy during treatment resulting in discontinuation of initial therapy Unevaluable outcome* (Composite strategy)
 
Intercurrent events that occur after adequate** completion of therapy:
 
6. Death except from violent or accidental cause (e.g., road traffic accident) Unfavorable outcome (Composite strategy)
 
7. Violent or accidental death Unevaluable outcome* (Hypothetical strategy)
 
8. Extension of treatment beyond the nominal duration except to make up missed doses Unfavorable outcome (Composite strategy)
 
9. New TB diagnosis due to a new strain of Mtb Unevaluable outcome* (Hypothetical strategy)
	
Participants lost to follow-up after the treatment phase with their last available TB culture being negative are considered unevaluable and are censored at the time of the last visit.
 
Participants who experience violent or accidental death are considered to have an unevaluable outcome and will be censored at the time of their last follow-up visit.
 
Participants reinfected with a new strain of Mtb are considered to have an unevaluable outcome and will be censored at the time of their last follow-up visit.
 
Participants who become pregnant during their assigned active treatment and who stop their assigned treatment are considered to have an unevaluable outcome and will be censored at the time of the last treatment dose received.

* See handling of missing data for imputation rules for unevaluable outcomes
 
Population-level summary measure
 
Difference in cumulative probability of having a favorable clinical/bacteriologic outcome at 65 weeks after TB therapy initiation .
	
Analysis approach
 
Difference in cumulative proportion of participants at 65 week visit together with 90% and 95% two-sided confidence intervals. We will use the Kaplan-Meier estimator and Greenwood's estimate for the standard error.

\*\* Adequate completion of therapy is determined by the following definitions:

Definitions of Adequate Treatment Within 3-month Regimen (Arm 1 in the setting of this trial)

- Taken a total of at least 56 doses of allocated intensive phase treatment within 70 days of starting treatment
- AND taken at least 28 doses of continuation phase treatment within 49 days (7 weeks) of completion of the intensive phase
- AND missed no more than 21 doses of medication overall.

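### Definition B does not exempt the 13 weeks of RH that LOA #1 added to Arm 1, so a DSMB-directed extension counts as an unfavorable outcome in Arm 1 only

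*SAP*

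**What the plan says.** **LOA #1 (June 2023).** Item 3 (Schema, Regimen) sets out the revised course for Arm 1 participants on the experimental regimen as of 16 June 2023: the original 13 weeks, "then rifampicin/isoniazid (RH) for 13 weeks for a total of 26 weeks of study treatment". Item 1 attributes the addition to the DSMB recommendations. Arms 2 and C continue unchanged.

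**SAP v3.0 (October 2023).** The version history says this version was revised to align with LOA #1.

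- Section 2.1 still describes Arm 1 as 13 weeks of treatment. On the letter it says only that "LOA #1 also includes extended follow-up for some participants corresponding to new exploratory objectives".
- Section 3.2.1, definition A, counts as unfavorable an "extension of treatment beyond the nominal level (week 13 for Arm 1 and week 26 for Arm 2) due to clinically inadequate response". This is where the nominal level is given in weeks.
- Section 3.2.1, definition B, includes everything in A. It adds any "extension of treatment beyond the nominal level, except to make up missed doses", with no requirement that response be inadequate. Its loss-to-follow-up bullet also takes 13 weeks as the Arm 1 treatment phase.
- Section 5.1.2, definition B table, repeats the extension rule as intercurrent event 8, under events after adequate completion of therapy: "Extension of treatment beyond the nominal duration except to make up missed doses Unfavorable outcome (Composite strategy"). The missing-data column says that participants with an extension, restart or change "are considered to have an unfavorable outcome and the event time is the time of the treatment modification".

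**The concern.** The extra RH was triggered by a recommendation for the whole arm and a calendar date. It says nothing about how the individual participant responded. Definition B has one exception to its extension rule, for missed doses, and the LOA RH does not fit it. Applied literally, the rule turns an administrative decision into treatment failures, and only Arm 1 can have them.

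The Arm 1 minus Arm 2 difference under definition B would then partly measure who happened to be on treatment on 16 June 2023. The events fall at about week 13, so they would enter both the primary analysis report (data up to the last enrolled participant's week-26 visit, SAP 2.1) and the later week-65 analysis. LOA #1 item 9 also requires the definition B probability to be shown at every DSMB review.

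**Working it through.** **1. Does LOA RH exceed the nominal level?** The regimen segments in LOA #1 item 3 give 2 + 6 + 5 = 13 weeks, plus 13 weeks of RH = 26 weeks, which reproduces the letter's total. Against the SAP's nominal levels:

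- Arm 1 with LOA RH: 26 − 13 = 13 weeks over, none of it make-up of missed doses.
- Arm 2: 26 − 26 = 0 weeks over.

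**2. Which definition is triggered?** Definition A requires a clinically inadequate response, so LOA RH alone is not an event. Definition B has no such condition, so it is an event, dated at the start of RH (about week 13). Definition B also has a bullet on changing a drug. That is a secondary route only, because the 5.1.2 table lists it among events during therapy.

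**3. Who is affected?** LOA #1 says accrual paused in April 2023 without giving the day. Those still on treatment at 16 June 2023 enrolled:

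- on or after 17 March 2023 if on schedule (16 June minus 91 days);
- on or after 17 February 2023 if they used all the time allowed in the Arm 1 adequate-treatment definition (70 + 49 = 119 days).

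| Start of window | Pause 1 April | Pause 30 April |
|---|---|---|
| 17 March | 15 days (2.1 weeks) | 44 days (6.3 weeks) |
| 17 February | 43 days (6.1 weeks) | 72 days (10.3 weeks) |

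The documents give neither the number on treatment at that date nor the number enrolled.

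**4. Effect per participant.** Each affected participant who would otherwise be favorable adds 1/n to the Arm 1 unfavorable proportion: 1/110 = 0.9 points at the planned Arm 1 size (SAP 2.4), or 1/60 = 1.7 points at an assumed 60 after early closure.

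**5. Effect by share affected.** Let f be the share of Arm 1 starting LOA RH and u the underlying unfavorable risk, both assumed. As written, the Arm 1 proportion is u + (1 − u)f, so the rise is f(1 − u). This takes follow-up as complete, in which case the Kaplan-Meier estimate equals the simple proportion, and takes u to be the same in the affected group as in the rest of Arm 1.

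| f | u = 0.05 | u = 0.20 | u = 0.35 |
|---|---|---|---|
| 2% | +1.9 | +1.6 | +1.3 |
| 5% | +4.75 | +4.0 | +3.25 |
| 10% | +9.5 | +8.0 | +6.5 |
| 15% | +14.25 | +12.0 | +9.75 |

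(percentage points)

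In counts, with k affected among n, the rise is k(1 − u)/n. For assumed n = 80, u = 0.12 and k = 6 it is 6 × 0.88/80 = 6.6 points (12.0% becomes 18.6%).

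**6. Scale.** With assumed risks of 0.20 and 0.10, the 90% CI half-width for the difference is:

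- planned 110 and 55: 1.645 × √(0.16/110 + 0.09/55) = 9.1 points;
- assumed 60 and 30: 1.645 × √(0.16/60 + 0.09/30) = 12.4 points.

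**The case against.** The best counter-argument is that LOA #1 amended the regimen itself. It calls the full 26 weeks study treatment and says Arm 1 treatment duration was revised. If nominal means whatever the protocol now assigns, LOA RH is not an extension, and event 8 does not apply because therapy is still under way. A strictly literal reading of definition B is also implausible elsewhere. Its drug-change bullet would catch the planned step-down after week 8 in both arms, which nobody would code as failure. On this view the modification rules are to be read relative to the assigned regimen.

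That may well be the sponsor's intention, and the drug-change route is weak for this reason. But the SAP gives the Arm 1 nominal level as week 13, in a version written after the letter. Adopting 26 weeks silently would also move other rules. A participant in this group lost at week 18 with a negative last culture is unevaluable under a 13-week treatment phase and unfavorable under a 26-week one. Either reading needs text.

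Three further points stand. The full protocol definition (10.2.4B) and the Analysis Implementation Plan were not available, so an exemption there cannot be excluded. The sizes above are illustrative, and at 60 and 30 participants every u = 0.20 figure lies inside the CI half-width. The consequence is also limited: definition B is secondary and estimated without a test, definition A is reported beside it, LOA #1 bases monitoring of unfavorable outcomes on A, and the distortion runs against Arm 1 in a trial already closed for treatment failure and recurrence.

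**Conclusion.** The concern holds. On the wording supplied, RH given under LOA #1 is an unfavorable definition B outcome at about week 13, in Arm 1 only. The bias has a known direction but an unknown size: +1.3 to +14.25 points over assumed shares of 2% to 15% and risks of 0.05 to 0.35, and zero in Arm 2. It rests on the SAP's week-13 nominal level being applied as stated and on no exemption existing in the documents not supplied.

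The primary efficacy analysis through week 12 is untouched. Definition A does not count LOA RH as an event. Keeping that follow-up is defensible as treatment policy, in line with how its table handles failure to complete treatment, but the SAP should state it. This should be fixed before the analysis; it does not threaten the trial's primary conclusion.

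**What to change.** 1. Reconcile the SAP's nominal-duration wording with LOA #1. State in 3.2.1 and in the definition B table of 5.1.2 (event 8, the drug-change event and the missing-data column) that RH given under LOA #1 is neither an unfavorable extension nor a drug change.
2. For this group, state which treatment-phase length governs the loss-to-follow-up rule and which adequate-treatment definition applies.
3. List LOA RH as its own intercurrent event under both A and B, with the strategy named. For A this may simply be treatment policy.
4. Report how many Arm 1 participants started LOA RH. SAP 6.4 already tabulates extensions and changes, so a separate line is enough.
5. Present a treatment-policy estimate and one censored at the start of RH, with the main one chosen in advance. The first mixes 13- and 26-week recipients in Arm 1; the second targets the 13-week regimen. Censoring is plausibly non-informative because RH was assigned by calendar date.

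The cost is SAP wording, one derived flag and one additional estimate for each definition. The censored version gives up as much as 65 − 13 = 52 weeks of follow-up per affected participant, including their recurrence window. Items 1 to 3 remove the defect without item 5. None of this changes treatment.

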#### Unevaluable Outcome

- Participants lost to follow-up after treatment phase, and not assessable at the end of follow-up, with their last culture being negative for *Mtb*.
- Violent or accidental death.
- Participants re-infected with a new strain of *Mtb* confirmed by conventional molecular genotyping (as defined by MIRU and IS6110 typing).
- Women who become pregnant during their assigned active treatment and stop their assigned treatment.

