##### Favorable Outcome (any one of the following scenarios)

- Participants with liquid culture negative status at week 65.
- Participants without signs or symptoms of ongoing active TB and are unable to produce a sputum specimen at 65 weeks.
- Participants who at the end of the follow-up period are clinically without symptoms/signs of ongoing active TB and produce a sputum specimen that is contaminated in two liquid cultures without evidence of TB.

For any of the above to be considered favorable, participants must not already have been considered unfavorable, as defined below.

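### In composite efficacy definition B, a non-completer lost after the treatment phase with a negative last culture is both an event and a censored observation

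*SAP*

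**What the plan says.** SAP 3.2.1 defines outcome B by three lists. Besides everything unfavorable under A, the B unfavorable list adds, among other things:

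- "Participants lost to follow-up during treatment phase of each Arm (i.e., 13 weeks and 26 weeks for Arms 1 and 2, respectively"). This fixes the treatment phase as a calendar period.
- "Participants failing to complete treatment (see below for Definitions of Adequate Treatment) and not assessable at the end of the follow-up period". There is no condition on the last culture or on when the participant was lost.

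The B unevaluable list begins with "Participants lost to follow-up after treatment phase, and not assessable at the end of follow-up, with their last culture being negative" for *Mtb*. There is no condition on adequate treatment.

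The B table in SAP 5.1.2 repeats both rules under missing data and attaches times to them. On one side, "Participants failing to complete treatment and not assessable at the end of the follow-up period are considered to have an unfavorable outcome", with the event at the last dose received. On the other, "Participants lost to follow-up after the treatment phase with their last available TB culture being negative are considered unevaluable and are censored", at the last visit.

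The ranking sentence in 3.2.1 belongs to the favorable list: to be favorable, "participants must not already have been considered unfavorable". It does not mention unevaluable. The estimator for B is Kaplan-Meier at week 65 with Greenwood standard errors.

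**The concern.** Consider a participant who does not meet the adequate-treatment definition, is still seen after week 13 (Arm 1) or week 26 (Arm 2), and is then lost with a negative last culture. One rule makes this an event at the last dose; the other makes it a censored observation at the last visit. Two programmers could each follow the SAP to the letter and report different week-65 proportions.

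Definition B differs from A because it brings treatment completion into the outcome, and this overlap falls on non-completers. Censoring them assumes that they would have fared like those still followed, whereas the unfavorable list says that they have already failed. The effect is to raise the favorable proportion. SAP 6.7 puts outcome 3.2.1 B in the primary analysis report, and the Letter of Amendment (change to protocol section 10.5.1) sends the definition 10.2.4B estimate to every DSMB review.

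**Working it through.** The plan gives no figure to reproduce; the check is on classification, followed by an illustration of size.

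**1. Which participants meet both lists?** Take everyone not assessable at week 65, setting re-infection aside, and cross timing of loss, adequacy of treatment and last culture (2 × 2 × 2 = 8 combinations; the first row holds four).

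| Lost | Treatment adequate | Last culture | Unfavorable rule met | Unevaluable rule met |
|---|---|---|---|---|
| During phase | either | either | yes | no |
| After phase | yes | negative | no | yes |
| After phase | yes | positive | yes | no |
| After phase | no | negative | **yes** | **yes** |
| After phase | no | positive | yes | no |

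Exactly one combination meets both.

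**2. Can it occur?** The adequate-treatment windows in SAP 3.2.1 run past the treatment phase:

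- Arm 1: 70 + 49 = 119 days = 17 weeks, against a 13-week phase.
- Arm 2: 70 + 154 = 224 days = 32 weeks, against a 26-week phase.

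A participant lost at week 15 (Arm 1) or week 29 (Arm 2) and still short of doses qualifies. Making up missed doses is not itself unfavorable, so no other rule need settle the case. Someone who stopped early, kept attending and was lost later also qualifies.

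**3. Size.** Planned arms are about 110 and 55 (SAP 2.4). An early event adds about 1/n to the unfavorable estimate: 1/110 = 0.9 points and 1/55 = 1.8 points. Censoring adds almost nothing.

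The following inputs are assumptions, not in the documents: 22 other failures in Arm 1 (5, 5, 4, 4, 4 at weeks 17, 22, 26, 34, 42) and 3 in Arm 2 (weeks 30, 34, 42); last dose at week 12 / 24; last visit at week 34 / 42.

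Four overlapping participants, in Arm 1 only:

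- As events: Arm 1 = 26/110 = 23.6%; Arm 2 = 3/55 = 5.5%; difference 18.2 points.
- As censored: Arm 1 survival is 92/110 through week 34. Four then leave, so 88 are at risk at week 42 with 4 failures. 1 − (92/110)(84/88) = 20.2%; difference 14.7 points.

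With the Greenwood standard error of each arm, 90% CI = difference ± 1.645 × √(SE₁² + SE₂²):

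| Overlap, Arm 1 / Arm 2 | Scored as events: Arm 1, Arm 2, difference (90% CI) | Censored: Arm 1, Arm 2, difference (90% CI) |
|---|---|---|
| 4 / 0 | 23.6%, 5.5%, 18.2 (9.8 to 26.5) | 20.2%, 5.5%, 14.7 (6.6 to 22.8) |
| 4 / 2 | 23.6%, 9.1%, 14.5 (5.3 to 23.8) | 20.2%, 5.5%, 14.7 (6.6 to 22.8) |
| 0 / 2 | 20.0%, 9.1%, 10.9 (2.0 to 19.9) | 20.0%, 5.5%, 14.5 (6.5 to 22.6) |

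Varying the other Arm 1 failures from 10% to 30% keeps the shift at 0.8 to 0.9 points per Arm 1 participant.

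**The case against.** The best reply is that the text already points to unfavorable. Loss during the phase has its own bullet, and a positive culture when last seen is unfavorable under A and carried into B. If the unevaluable rule took the culture-negative non-completers lost later, the bullet on failing to complete treatment would cover almost no one. The last dose also ordinarily precedes the last visit, so a first-event convention would give an event. Both arguments are sound and show the likely intent, but they are inferences. The SAP states no such convention for this outcome, and its censoring sentence is as explicit as its event sentence.

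Neither of two possible escapes works. After the treatment phase cannot simply mean after completing treatment, because the phase is defined in weeks. The table heading on adequate completion governs a list of intercurrent events that does not include loss to follow-up.

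A reader might infer that violent or accidental death and pregnancy during treatment are equally unresolved, since such participants have usually not completed treatment either. The documents do not support that: the B table names both as unevaluable and gives each its own censoring time. Their composite-strategy label, where the A table says hypothetical, is a terminology slip that changes no estimate.

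A reader might also infer that censoring strips treatment completion out of B. It does not. Loss during treatment, re-starts, drug changes and extensions other than for missed doses remain unfavorable under either reading.

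**Conclusion.** The conflict is real but narrow: two explicit rules give one class of participant incompatible codings, and no rule in the SAP ranks unfavorable against unevaluable for that class. Unfavorable is the likely intent; applying the censoring sentence literally would bias the favorable proportion under B upward.

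The per-participant effect depends only weakly on the assumptions; the total effect depends on a count that the documents do not give. The windows show that the case can arise, not that it is common: they are outer limits, and someone lost in weeks 13 to 17 may already have the 56 + 28 = 84 doses required. Nor do the documents support a claim that the arm comparison is necessarily distorted. With overlap in proportion to arm size, the difference is 14.5 against 14.7 points, although each arm's own proportion moves by about 3.5 points. Arms left smaller by early closure would make each participant count for more.

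The supplied protocol file is the Letter of Amendment, so section 10.2.4 could not be checked for a ranking rule, nor could the Analysis Implementation Plan. B is a secondary outcome reported by estimate and interval, and the primary efficacy analysis is untouched. The wording should be corrected before the week-65 analysis is run.

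**What to change.** In the first bullet of the B unevaluable list (SAP 3.2.1) and the matching sentence in the missing-data column of the B table (SAP 5.1.2), insert *who completed adequate treatment* after the opening word. A non-completer who is not assessable at the end is then unfavorable, with the event at the last dose, unless one of the specifically named unevaluable events applies. Check protocol section 10.2.4B and the Analysis Implementation Plan for the same wording.

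As an editorial matter only, the strategy labels of intercurrent events 2 and 5 in the B table can be changed to hypothetical.

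The cost is a wording change, with no new data. If the programs already score these participants as unfavorable, no result changes. If they censor them, the favorable proportion under B falls by the per-participant amounts shown above.
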